1.0 Introduction and Study Rationale

1.1 Overview

There is great need for new therapeutic options for patients with hepatocellular carcinoma (HCC). This study will assess the feasibility of a novel theranostic approach to hepatocellular carcinoma (HCC) using [⁶⁸Ga]DOTATATE, a recently FDA-approved positron emission tomography (PET) ligand for imaging somatostatin receptor (SSTR) positive tumors. This PET tracer is in routine clinical use for neuroendocrine tumors (NET) but to our knowledge has not been systematically applied to HCC. The objective of this study is to measure the frequency of SSTR positivity in hepatocellular carcinoma using [⁶⁸Ga]DOTATATE-PET. We hypothesize that [⁶⁸Ga]DOTATATE-PET will be positive in at least 20% of patients with HCC. If this current study shows a substantial fraction HCCs have moderate to high SSTR levels based on PET imaging, this result would justify future studies evaluating targeted radionuclide therapy (TRT) with the therapeutic SSTR ligand [¹⁷⁷Lu]DOTATATE which was recently FDA approved for treating SSTR-positive NETs arising from the gastrointestinal tract.

Study objective: Determine the frequency of somatostatin receptor positivity in hepatocellular carcinoma using [⁶⁸Ga]DOTATATE-PET

Hypothesis: [⁶⁸Ga]DOTATATE PET will be positive in at least 20% of patients with hepatocellular carcinoma (HCC).

In this study, patients with treatment-naïve HCC (n=15) and patients with previously treated HCC being referred for systemic chemotherapy and/or best supportive care (n=15) will be enrolled. Patients will undergo a single whole body [⁶⁸Ga]DOTATATE-PET/MRI to assess SSTR positivity of their HCCs. The percentage of patients with HCCs showing activity in their HCC greater than liver and/or spleen will be calculated.

1.2 Background and Rationale

HCC is the most common type of liver cancer and frequently arises in the background of hepatic cirrhosis. HCC and other liver cancers accounted for an estimated 40,710 cases and 28,920 deaths in the United States in 2017.[1] The five-year survival for patients with liver cancer confined to the liver is estimated at 31.1%, but prognosis for tumors that spread outside of the liver is much worse with 10.7% five-year survival for patients with regional lymph node metastases and 2.8% for patients with distant metastases.[1] The definitive treatment for HCC is liver transplantation, but frequently patients do not choose to undergo transplantation or are deemed ineligible. In recent years, locoregional therapies for HCC have become increasingly utilized, including transarterial chemoembolization, percutaneous ablation, external beam radiation, and radioembolization with ⁹⁰Y-labeled microspheres. These treatments are frequently utilized as a bridge to transplantation, but can also be used for definitive therapy for HCC. However, once the tumor has been found to spread beyond the liver and adjacent lymph nodes, few systemic treatment options remain available to patients. The first systemic treatment option for HCC was sorafenib, a tyrosine kinase inhibitor which was approved in 2007 for treatment of advanced HCC

following a trial that demonstrated a 44% improvement in median overall survival when compared to placebo.[2] However, sorafenib is frequently not well tolerated by patients with side effects experienced by approximately 64.9% of patients, with diarrhea, hand-foot-skin reaction, nausea, and fatigue being the most common.[3] As a result, in 2017 a second-line tyrosine kinase inhibitor (regorafenib) was approved in patients with advanced HCC who have been unable to tolerate or progressed on sorafenib.

[⁶⁸Ga]DOTATATE (tradename NETSPOT) is a peptide-based radiopharmaceutical for positron emission tomography (PET) that was approved for clinical use in the United States in 2016 for the evaluation of somatostatin receptor (SSTR)-positive neuroendocrine tumors (NETs). This PET tracer binds to SSTRs on the surface of tumor cells with the highest affinity for the SSTR2 receptor which is overexpressed in neuroendocrine tumors. In patients with metastatic NETs, somatostatin analogues (e.g. octreotide and lantreotide) are a mainstay in control of symptoms, but do not treat the underlying metastatic disease. In 2018, the FDA approved a therapeutic analogue of DOTATATE ([¹⁷⁷Lu]DOTATATE, tradename Lutathera) for the treatment of SSTR-positive gastroenteropancreatic NETs. A key concept is that [⁶⁸Ga]DOTATATE-PET is used to evaluate metastatic NETs for SSTR expression and use this information to select potential candidates for [¹⁷⁷Lu]DOTATATE therapy. This theranostic approach can potentially be applied to other tumors that express adequate levels of SSTR.

SSTR expression has previously been demonstrated in the setting of HCC to varying degrees. A study of 53 resected HCCs demonstrated that membrane SSTR2 was reliably detected in HCC and could serve as a potential therapeutic target.[4] Multiple tissue-based studies demonstrate SSTR positivity in 20-50% of HCCs.[4-6] Additionally, SSTR2 expression in HCC was positively correlated with cytokeratin 19-9 expression, serum alpha-fetoprotein level, and poor differentiation, all of which are poor prognostic markers for patients with HCC.[4, 7, 8] Additional studies have confirmed SSTR expression in HCC with varying distributions of the SSTR receptor subtype expression.[5, 6] However, the fraction of HCCs have high enough levels of SSTR for [¹⁷⁷Lu]DOTATATE therapy has not yet been assessed. Therefore, it is our aim to use [⁶⁸Ga]DOTATATE-PET/MRI to assess tumor SSTR expression in patients with HCC before and after locoregional therapy. This research plan is a critical prerequisite for determining the feasibility of this theranostic approach to treating HCC. If we obtain positive results, these data will be critical for designing a combined imaging and therapeutic study in HCC using DOTATATE.

2.0 Study Objectives

Specific Aim 1: Determine the frequency of somatostatin receptor positivity in hepatocellular carcinoma using [⁶⁸Ga]DOTATATE-PET

Hypothesis 1: [⁶⁸Ga]DOTATATE PET will be positive in at least 20% of patients with hepatocellular carcinoma (HCC).

Liver transplantation is the only curative therapy for HCC and is an option for a selected subset of HCC patients. For those who are not candidates for transplantation, locoregional therapies with limited efficacy are available such as percutaneous ablation,

arterial chemoembolization, and Y-90 microsphere radionuclide therapies. There are few options for patients who progress or are not candidates for these therapies. The first line systemic therapy is sorafenib, a tyrosine kinase inhibitor. Sorafenib is often not well tolerated due to its side effects and there is need for additional systemic treatments.

3.0 Investigational Plan

3.1 Study Design

The project will be a pilot prospective IRB-approved HIPAA-compliant study that will enroll 15 patients with untreated HCC and 15 patients with previously treated HCC. These patients will be identified at weekly multidisciplinary hepatobiliary conference in collaboration with liver transplant surgery, interventional radiology, diagnostic radiology, hematology/oncology, gastroenterology, and radiation oncology. Patients will undergo standard-of-care treatment based on recommendations of hepatobiliary tumor board. The preferred imaging modality will be PET/MRI, owing to its superior soft tissue characterization of the liver and abdominal soft tissues when compared to non-contrast CT performed for PET/CT. However, understanding that patients may have large volume ascites or claustrophobia, PET/CT may be utilized as an alternative in select patients at the discretion of the Principal Investigator. The study will be performed within 4 weeks of most recent conventional anatomic imaging with either CT or MRI to minimize the potential to alter clinical management on the basis of the CT or MRI portion of the research examination.

3.2 Study Population

- Patients with treatment naïve hepatocellular carcinoma and patients with previously treated hepatocellular carcinoma being referred for systemic chemotherapy and/or best supportive care

3.3 Inclusion Criteria

- Known diagnosis of hepatocellular carcinoma, either by imaging criteria or pathology on biopsy
- Standard of care liver MRI or CT demonstrating viable HCC based on arterial contrast enhancement measuring at least 1.5 cm in largest axial dimension

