3.4 Exclusion Criteria

- History of neuroendocrine tumor or other SSTR-positive tumor
- Current treatment with octreotide or lantreotide
- Interval locoregional therapy or new systemic therapy between standard of care liver MRI or CT study showing viable HCC and [⁶⁸Ga]DOTATATE-PET

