5.0 Study Parameters

5.1 Primary Endpoint

- Percentage of patients with moderate to high binding of [⁶⁸Ga]DOTATATE on PET examination
- Concordance between [⁶⁸Ga]DOTATATE PET results and liver MRI results

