6.4 Statistical Analysis Plan

This study will largely be exploratory and descriptive. For all clinical and histological evaluations as well as imaging parameters, we will generate summary tabulations of the number of observations, mean, standard deviation, median, minimum, and maximum for continuous variables, and the frequency and percentage for categorical variables. Analyses will be primarily descriptive and graphical in nature. The count, and percentage of patients with HCCs showing activity in their HCC greater than liver and/or spleen will be estimated using Clopper-Pearson (exact) method along with two-sided 95% CI. The estimation will be provided for all 30 patients first, and then by treatment-naïve or not.

Concordance between [⁶⁸Ga]DOTATATE PET results and liver MRI results for patients with SSTR-positive HCC and positive [⁶⁸Ga]DOTATATE PET, intrahepatic and extrahepatic disease will be assessed on MRI/CT alone first, with confidence in interpretation rated on a 1-5 scale (1 = negative, 5 definite). Following this, fused PET/CT or PET/MRI images will be assessed and rated on the same 1-5 scale. Scale 3-4

is defined as positive. The agreement (concordance) between nominal (e.g. scale 1-5) or binary outcome (positive or negative) of [⁶⁸Ga]DOTATATE PET results and liver MRI results will be assessed using Cohen's kappa coefficients with one-side 95% confidence intervals. Based on values of Cohen's kappa, the agreement will be considered as poor (>0.2), fair (0.21-0.40), moderate (0.41-0.60), good (0.61-0.80), and very good (0.81-1.0) ([Dtsch Arztbl Int. Concordance Analysis. 2011 Jul; 108\(30\): 515-521. PMID: 21904584](#)). Bland-Altman diagrams will be used to evaluate agreement for other continuous imaging variables between these two methods. All statistical analysis will be carried on SAS v9.4.

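### Because entry selects on a positive MRI/CT, the binary patient-level kappa for intrahepatic disease (5.1, 6.4) will be about 0 or undefined, however the tracer performs

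*Combined protocol and SAP*

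**What the plan says.** Section 5.1 lists two primary endpoints. The first is the percentage of patients with moderate to high binding. The second is concordance between DOTATATE "PET results and liver MRI results".

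Three provisions decide what the anatomic imaging can show:

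- Section 3.3 requires "Standard of care liver MRI or CT demonstrating viable HCC based on arterial contrast enhancement", with a largest axial dimension of 1.5 cm or more.
- Section 3.4 excludes "Interval locoregional therapy or new systemic therapy between standard of care liver MRI or CT study showing viable HCC and" the PET.
- Section 3.1 places the study scan within 4 weeks of the latest conventional CT or MRI.

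Section 6.4 gives the analysis. "The agreement (concordance) between nominal (e.g. scale 1-5) or binary outcome (positive or negative) of" the PET and the liver MRI "will be assessed using Cohen's kappa coefficients with one-side 95% confidence intervals", and the value is then given a verbal label from poor to very good. On the ratings, section 6.4 says that "intrahepatic and extrahepatic disease will be assessed on MRI/CT alone first, with confidence in interpretation rated on a 1-5 scale (1 = negative, 5 definite"), after which the fused images are rated on the same scale. It introduces these reads for patients with a positive PET. It does not say whether the unit for kappa is the patient, the lesion or the site.

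The liver MRI is a new contrast scan in the PET/MRI session (4.6.2). Patients who go to PET/CT get a noncontrast CT for localisation (4.6.3).

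**The concern.** Kappa measures agreement beyond chance, so it needs both results to vary between patients. Here eligibility selects on one of them. An untreated viable tumour of at least 1.5 cm, seen within the previous 4 weeks, should still be visible on the study liver MRI, and no patients without HCC are planned. For intrahepatic disease read as positive or negative per patient, the anatomic margin is then close to constant.

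The restriction of the reads to PET-positive patients is a separate problem. Lifting it so that all 30 patients are rated would still leave the MRI side positive in nearly all of them.

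At stake is how a listed primary endpoint would be reported. A trial that met its own 20% hypothesis could publish poor agreement between PET and MRI, and that label would reflect patient selection, not the tracer. If MRI is positive in everyone, raw agreement is no better: it equals the PET-positive fraction, which the first endpoint already reports.

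**Working it through.** **The plan's own figures.** Section 6.2 gives Clopper-Pearson 95% intervals at 20% positivity. For 6/30 the calculation gives 7.71% to 38.57%, and for 3/15 it gives 4.33% to 48.09%. Both match the stated 7.7% to 38.6% and 4.3% to 48.1%. The plan states no expected kappa and no precision for it.

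**Inputs.** n = 30 and 20% PET-positive, that is 6 patients (6.2). MRI positive in all or nearly all patients is an assumption drawn from 3.1, 3.3 and 3.4.

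**Formula.** Let a = MRI+ PET+, b = MRI+ PET−, c = MRI− PET+, d = MRI− PET−. Then

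- Po = (a + d)/n
- Pe = [(a + b)(a + c) + (c + d)(b + d)]/n²
- kappa = (Po − Pe)/(1 − Pe)

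**1. MRI positive in all 30, PET positive in k.** Po = k/30. Pe = [30·k + 0·(30 − k)]/900 = k/30. The numerator is 0, so kappa = 0 for every k from 0 to 29. At k = 6, Po = Pe = 0.200. At k = 30, Po = Pe = 1 and kappa is 0/0, undefined.

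**2. A few study MRIs read negative, 6 PET-positive.** The counts of negative MRIs are illustrative.

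| MRI-negative patients | Po | Pe | kappa |
|---|---|---|---|
| 1, PET-negative | 7/30 = 0.233 | (29·6 + 1·24)/900 = 0.220 | 0.017 |
| 2, PET-negative | 8/30 = 0.267 | (28·6 + 2·24)/900 = 0.240 | 0.035 |
| 3, PET-negative | 9/30 = 0.300 | (27·6 + 3·24)/900 = 0.260 | 0.054 |
| 6, PET-negative | 12/30 = 0.400 | (24·6 + 6·24)/900 = 0.320 | 0.118 |
| 1, PET-positive | 5/30 = 0.167 | (29·6 + 1·24)/900 = 0.220 | −0.068 |
| 2, PET-positive | 4/30 = 0.133 | (28·6 + 2·24)/900 = 0.240 | −0.140 |

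Every value is below 0.2. Section 6.4 prints the bound of its poor band with a greater-than sign; the next band starts at 0.21, so I take poor to mean 0.2 or less.

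**3. PET-positive subset only, as 6.4 describes, with 6 patients.** If the MRI/CT-alone read and the fused read are both positive in all 6, Po = Pe = 1 and kappa is undefined. If one anatomic read is negative and all fused reads are positive, Po = 5/6, Pe = (5·6 + 1·0)/36 = 5/6 and kappa = 0.

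**4. Where the result does not carry over.** These tables are assumed, to show only that kappa can move.

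- Extrahepatic disease, a/b/c/d = 5/3/1/21: Po = 26/30 = 0.867, Pe = (8·6 + 22·24)/900 = 0.640, kappa = 0.63.
- The 1-5 ratings in 6 patients, 3,4,4,5,5,5 against 4,4,5,5,5,5: Po = 4/6, Pe = (2·2 + 3·4)/36 = 0.444, kappa = 0.40.

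**The case against.** The case on the other side has five parts.

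- **The scan.** Entry fixes the standard-of-care scan, but the ratings use the study scan: a new liver MRI, or a noncontrast CT on which arterial enhancement cannot be assessed. A reader might infer that the anatomic result is fixed at positive in every enrolled patient. The documents do not support that. What stands is that nearly all study MRIs should be positive, and step 2 shows that a few negatives leave kappa close to 0. Negative reads on the noncontrast CT would partly reflect the missing contrast.
- **The comparison.** The reads in 6.4 set MRI/CT alone against fused images in PET-positive patients, so the 30-patient table of MRI against PET is only one reading of an ambiguous text. That is fair. On the other reading (step 3), the binary intrahepatic kappa is undefined or 0, so the conclusion survives.
- **Scope.** Extrahepatic disease is also rated, the 1-5 scale may be used, no unit is stated, and entry guarantees only one lesion of at least 1.5 cm. A reader might infer that the whole concordance endpoint is uninformative. It is not, as step 4 shows. The point is confined to the binary, patient-level, intrahepatic analysis.
- **Consequence.** Section 6.2 plans no formal hypothesis test, section 6.4 calls the study largely exploratory, and the only go-forward criterion is 20% PET positivity. No decision rests on kappa. This limits the harm to a misleading or missing result on a listed primary endpoint.
- **The replacement.** The proportion of viable lesions that are PET-positive is close to a lesion-level form of the first endpoint. True, but it answers the question in 6.1 about HCC seen on anatomic imaging, and the discordance counts add information that this kappa cannot.

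**Conclusion.** The concern holds for the binary, patient-level, intrahepatic kappa. That statistic will be about 0 (exactly 0 for 0 to 29 PET-positive of 30 if MRI is positive in all; between −0.14 and 0.12 in the departures tried) or undefined. It cannot tell a useful tracer from a useless one.

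The verdict rests on three assumptions: untreated viable HCC of at least 1.5 cm is still read as positive on nearly every study MRI; the binary analysis is made per patient; and a definite lesion (score 5) counts as positive. Section 6.4 literally defines only scores 3-4 as positive. Under that wording the anatomic result could vary, but as an artefact of the cut-off and not as evidence about concordance.

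Two stronger inferences fail. Kappa is not 0 whatever PET shows, because it is undefined when every analysed patient is positive on both sides. Nor is section 3.3 a design error: requiring viable HCC suits an estimate of how often HCC is SSTR-positive. The fault lies in the choice of agreement statistic in 5.1 and 6.4.

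**What to change.** In 5.1 and 6.4, for intrahepatic disease:

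- Replace the binary patient-level kappa with the proportion of MRI/CT-viable HCC lesions of at least 1.5 cm that are PET-positive, in all scanned patients, with a confidence interval that allows for several lesions per patient (for example, by treating the patient as the cluster).
- Add counts of lesions seen on PET only and on MRI/CT only.
- State the anatomic reference: the study liver MRI or, for PET/CT patients, the entry contrast MRI/CT, because their study CT is noncontrast.

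Keep kappa only for extrahepatic disease, rated present or absent by site, and list it as secondary.

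The cost is a wording change plus lesion-level recording. No new scans or readers are needed. Anatomic lesions must also be recorded in PET-negative patients, which 4.6.4 and 6.4 do not now describe, and the trial would no longer report a single patient-level kappa as a primary endpoint.

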3.4 Exclusion Criteria

- History of neuroendocrine tumor or other SSTR-positive tumor
- Current treatment with octreotide or lantreotide
- Interval locoregional therapy or new systemic therapy between standard of care liver MRI or CT study showing viable HCC and [⁶⁸Ga]DOTATATE-PET

3.5 Withdrawal Criteria

- Given that enrollment in this study will involve a single imaging exam, no withdrawal criteria will be used

- Patient charts will be followed for 12 months following PET to evaluate for outcomes

3.6 Replacement of Patients

- Given that enrollment in this study will involve a single imaging exam, no replacement of patients will be used

3.7 Study Duration

- Study enrollment and imaging will take place over 12 months

3.8 Safety Monitoring

3.8.1 Data and Safety Monitoring Plan

Patients will be informed of the extent to which their confidential health information generated from this study may be used for research purposes. Following this discussion, they will be asked to sign the HIPAA form and informed consent documents. The original signed document will become part of the patient's medical records, and each patient will receive a copy of the signed document. The use and disclosure of protected health information will be limited to the individuals described in the informed consent document. PET/MRI and PET/CT scans will be loaded into a separate password-protected image storage system that will not appear on the PACS utilized in clinical practice.

3.8.2 Ethical Considerations

Given that the study involves a single imaging session with either PET/MRI or PET/CT and the expected age of the enrolled adult patients, ethical concerns regarding additional radiation exposure are minimal. If an unexpected potentially medically important finding is detected through participation in this study, the referring provider will be notified of the results to consider pursuing additional imaging or other diagnostic procedure.

4.0 Study Procedures

4.1 Informed Consent Procedure

All participants must be provided a consent form describing the study with sufficient information for each participant to make an informed decision regarding their participation. Participants must sign the IRB-approved informed consent form prior to participation in any study specific procedure. The participant must receive a copy of the signed and dated consent document. The original signed copy of the consent document must be retained in the medical record or research file.

4.2 Patient Registration

Enrollment in the study will be available after the patient has been seen by their treating physician at UAB. The majority of these patients are expected to be seen in Liver Transplant clinic. However, all patients that meet enrollment criteria are eligible.

Registration in the study will be performed by a research coordinator from the UAB Department of Radiology. Participation in the study is voluntary and choosing not to participate will not affect patient care in any way.

4.3 Initiation of Study

The PET tracer [⁶⁸Ga]DOTATATE is FDA-approved for gastroenteropancreatic neuroendocrine tumors and routinely produced for standard-of-care clinical PET through the UAB Cyclotron Facility and Radiopharmacy. The preparation of [⁶⁸Ga]DOTATATE for this study will be identical to the procedure used for producing clinical dosages. Additionally, UAB currently is performing clinical [⁶⁸Ga]DOTATATE-PET scans, including PET/CT and PET/MRI. Therefore, the study can be initiated immediately following institutional and IRB approval.

4.4 Drug Information

[⁶⁸Ga]DOTATATE is a radiolabeled peptide-based analogue of octreotide that is FDA-approved PET imaging agent for use in patients with gastroenteropancreatic neuroendocrine tumors. The radiotracer targets somatostatin receptors with highest affinity for SSTR2, which has been shown to be overexpressed in hepatocellular carcinoma. The dosage of radiotracer administered to the patient is an intravenous weight-based dose of 2 MBq/kg (0.054 mCi/kg) up to a dose of 200 MBq (5.4 mCi). This results in an effective dose of up to 4.2 mSv (420 mrem) to the patient, which is equal to 1.4 years of natural background radiation exposure (3 mSv/yr).

